APHAB	Abbreviated Profile of Hearing Aid Benefit
BC	Bone conduction
CHL	Conductive Hearing Loss
CIP	Clinical Investigation Plan
CI	Confidence Interval
dB	Decibel
EC	Ethics Committee
ENT	Ear, Nose and Throat
FAS	Full Analysis Set
GEE	Generalized Estimating Equation
HL	Hearing Loss
Hz	Hertz
IC	Informed Consent
ICH	International Conference on Harmonization
ICH E3	ICH guideline E3: Structure and content of clinical study reports
ICH E6	ICH guideline E6: Guideline for Good Clinical Practice
ICH E9	ICH guideline E9: Statistical principles for clinical trials
IRR	Incidence Rate Ratio
IQR	Interquartile Range
MPO	Maximum Power Output
NR	No Response
PTA	Pure Tone Average
PPS	Per Protocol Set
QOL	Quality Of Life
SAP	Statistical Analysis Plan
SNR	Signal-to-Noise Ratio
SRT	Speech Recognition Threshold
SSD	Single-Sided Deafness
VT	Vibrotactile

3 Introduction

The Sophono Alpha 1 processor has gone through a series of upgrades (Alpha 2 and Alpha 2 MPO) while the implant with dual magnets remains relatively unchanged. Bench audiogram research and ancillary data presented at society meetings indicate an improved feedback-free gain with the Alpha 2 MPO device over earlier versions; however, to date no studies have been published. The aim of this study is to examine the long-term (implant duration three months or longer) audiologic, safety, and quality of life outcomes of subjects implanted with the Sophono bone conduction hearing implant and to compare the Alpha 2 to the Alpha 2 MPO sound processors. This SAP is based on Protocol Clinical Investigation Plan MDT16043ENT, Version 2.0. The SAP has been prepared in agreement with Medtronic internal procedures, and using the STROBE Statement¹ and ICH guidelines E3, E6 and E9 as guidelines.

4 Study objectives

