7.6 Derived variables

The statistical evaluations could use some derived variables calculated from collected data. All derived variables will be listed and reported.

New Variable	Derivation
Age at implant (years)	(Procedure date-Date of Birth)/365.25*
Time Diagnosis-Implant (months)	(Diagnosis date-Date of Implant)/365.25*
Device Exposure (days)	Study Evaluation/explant date – Procedure date*
Time to explant (days)	Explant date - Procedure date*
Derived Hz variables – method I	
In order to obtain the PTA for all the subjects, we will derive the Hz values according to the following rules: If the Hz value is collected in the OC CRF then the derived dB variables will be equal to the collected dB value.
 
Otherwise for the subjects that have no response (NR) at the limits of audiology testing for non-aided testing, we will derive the value, as agreed with the study team and audiologists, substituting a conservative dB value. In particular, if the NR limit is indicated then the derived Hz variable will be equal to the tested limit (e.g. if Hz value= NR105 then the derived Hz variable will be equal to 105), otherwise if the NR limit is not indicated then the derived Hz value will be equal to 100dB for the AC test and equal to 65dB for the BC test).

Derived Hz variables – method II	
Also, a second method will be applied. As agreed with the study team we will derive the Hz values according to the following rules:
 
If the Hz value is collected in the OC CRF then the derived dB variables will be equal to the collected dB value.
 
Otherwise, for the subjects that have no response (NR) at the limits of audiology testing for non-aided testing, we will calculate the mean and standard deviation values on the entire cohort of responders at any Hertz level (e.g. 500Hz, 1000Hz, ect.) taking into account the type of test (AC or BC). Then we will derive the values substituting the mean + 2 * Standard deviation at any NR measure (both NR and NRxxx) according to the test type (AC or BC) for the SSD cohort. We will use these measures to perform analysis on SSD subset and we will compare graphically these results with the results of the same cohort (SSD subjects) evaluated with the first substitution method.

New Variable	Derivation

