PTA (dB)	The PTA will be calculated as average of the derived audiogram Hz values. For the AC test all the available values at 250Hz, 500Hz, 1000Hz, 2000Hz, 3000Hz, 4000Hz and 8000Hz will be considered in the calculation. For the BC or Aided tests all the available values at 500Hz, 1000Hz, 2000Hz, 3000Hz and 4000Hz will be considered in the calculation. Missing or VT values will not be considered in the calculation.
Gain (dB) in the free-field pure tone audiology	Absolute difference between PTA values
Time to first AE (days)	Study Evaluation- First AE occurrence date ¹
Total time in hospital (days)	Discharge date – Admission date

¹ if more than one procedure or event, consider the date of the first one.

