7.10.1 Primary endpoint

The primary safety endpoint is the proportion of AEs related to the Sophono implant or surgery, which will be assessed through retrospective surgical chart review and prospective ENT exam. The primary safety endpoint will be evaluated on FAS. The AEs used for this endpoint are according to Investigator's determination of the event's relatedness to the device or surgery.

Adverse Event rates will be displayed together with their 95% confidence interval (95%CI) overall, by site and by type of event.

A time to first Adverse Event will be performed using survival analysis. The analysis will be supported by a Kaplan Meier curve indicating the number of patients at risk and any possible comparison of curves between groups will be done using the Log-Rank Test where appropriate.

Table x - Primary safety endpoint – Sophono Implant related Adverse Events rates

Figure x - Kaplan Meier estimate of first Sophono Implant related Adverse Event occurrence

Table x - Kaplan Meier estimate of first Sophono Implant related Adverse Event occurrence

The primary effectiveness endpoint is the absolute difference (gain) in the free-field pure tone audiometry assessed by PTA unaided (AC) and aided by the Alpha 2 MPO processor. The primary effectiveness endpoint will be evaluated on PPS.

The difference between unaided and aided measurements will be analyzed by means of paired (samples) t-test or Wilcoxon signed rank sum test according to the normal or non-normal distribution.

Additional analysis will be performed on:

- the "within indication" subset will exclude from the analysis subjects whose Prospective AC & BC tests do not meet the device indications for use.

- The subsets defined by implanted ear diagnosis. For the subject affected by SSD, analyses will be performed for both the derived variables (both NR substitution methods).

Table x - Primary effectiveness endpoint - Difference in PTA between unaided (AC) and aided by the alpha 2 MPO Processor (Audiogram Results Gain)

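### SAP 7.6 substitutes a limit for unaided no-response results but drops vibrotactile results as if untested, which can shift an ear's PTA and primary gain in either direction

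*SAP*

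**What the plan says.** SAP section 7.6 gives two ways to handle an unaided NR result.

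- **Method I, limit recorded:** "if the NR limit is indicated then the derived Hz variable will be equal to the tested limit".
- **Method I, no limit recorded:** "otherwise if the NR limit is not indicated then the derived Hz value will be equal to 100dB for the AC test", and 65 dB for bone conduction (BC). The stated purpose is to have a PTA for every subject, using a conservative value agreed with the audiologists.
- **Method II, SSD subset:** each NR is replaced by the responders' mean plus two standard deviations for that test type.

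VT appears in the abbreviation list only as "Vibrotactile". The PTA row of section 7.6 then says "Missing or VT values will not be considered in the calculation". That sentence follows the rules for air conduction (AC), BC and aided tests and is not restricted to any of them. The AC PTA averages whatever is available of seven frequencies (250 to 8000 Hz). The aided PTA averages whatever is available of five (500 to 4000 Hz).

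Under SAP 7.10.1 the primary effectiveness endpoint is the absolute difference between the unaided AC PTA and the PTA aided by the Alpha 2 MPO. The only planned check on these derivations concerns NR: "For the subject affected by SSD, analyses will be performed for both the derived variables (both NR substitution methods"). SAP 7.4 rules out imputation of missing data.

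**The concern.** A VT result means that the tone was felt rather than heard. Like NR, it says that a tone was presented and no hearing threshold was obtained. The SAP carries one of these results into the PTA as a limit and treats the other as a frequency never tested. It gives no reason for the difference, and the deletion sits badly with the stated aim of a PTA for all subjects.

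Three things follow:

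- Two ears with the same heard thresholds can get different unaided PTAs, and so different gains, only because of the code entered at the unheard frequencies.
- An ear whose AC results are all VT or missing has no unaided PTA and therefore no gain. The SAP sets no minimum number of frequencies for a PTA.
- Methods I and II both change NR values only, so comparing them cannot show what the VT rule does.

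The SAP also leaves open how a VT entry with a dB level fits the rule "If the Hz value is collected in the OC CRF then the derived dB variables will be equal to the collected dB value".

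**Working it through.** **The plan's own figure.** Protocol 13.1 gives 58.7 (SD 8.2) dB unaided and 29.7 (SD 8.2) dB aided, two-sided alpha 5%, power 95%, and 6 pairs. The difference is 58.7 − 29.7 = 29.0 dB. The SD of the paired difference is not stated. With an assumed correlation r it is 8.2 × √(2(1 − r)).

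- r = 0: SD 11.6. A paired t-test needs 5 pairs (power 98.2% at 5, 99.7% at 6).
- r = −0.5: SD 14.2. It needs 6 pairs.

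The stated 6 is therefore reproduced within the range of plausible correlations and is not in dispute. It matters here only as the scale: a 29 dB effect that very few pairs would detect.

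**Effect of deleting VT.** Let m of the seven AC frequencies be VT, let M be the mean of the other 7 − m, and let L be the value that would be substituted.

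- Deleted: PTA = M
- Substituted: PTA = ((7 − m)M + mL) / 7
- Deleted minus substituted = (m/7)(M − L)

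While the unaided PTA exceeds the aided PTA, the gain changes by the same amount. With the plan's own default L = 100 dB, and M and m assumed:

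| M (dB) | m = 1 | m = 2 | m = 3 |
|---|---|---|---|
| 58.7 | −5.9 | −11.8 | −17.7 |
| 70 | −4.3 | −8.6 | −12.9 |
| 80 | −2.9 | −5.7 | −8.6 |
| 90 | −1.4 | −2.9 | −4.3 |
| 100 (others NR at 100) | 0 | 0 | 0 |
| 105 (others NR105) | +0.7 | +1.4 | +2.1 |

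The sign also depends on L. With m = 2 and M = 100, the change is +5.7 dB for L = 80, 0 for L = 100 and −1.4 dB for L = 105.

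**Same ear, two codes.** Take five thresholds at 70 dB and two frequencies with no heard response.

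- Coded NR without a limit: (5 × 70 + 2 × 100) / 7 = 78.6 dB
- Coded VT: 70.0 dB

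The difference of 8.6 dB is 8.6/29.0, about 30% of the planning gain. If 10% to 30% of ears were affected in this way (an assumption), the mean gain would fall by 0.10 × 8.6 = 0.9 dB to 0.30 × 8.6 = 2.6 dB.

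**Seven against five frequencies.** Two invented ears, each with VT at 250 and 500 Hz:

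| Ear | Seven, VT as level | Seven, VT deleted | Five, VT as level | Five, VT deleted |
|---|---|---|---|---|
| SSD: VT 90 and 100, NR110 at the other five | 105.7 | 110.0 | (100 + 4 × 110)/5 = 108.0 | 110.0 |
| Mixed: VT 95 and 100, then 85, 80, 80, 85, 95 | 88.6 | 85.0 | (100 + 85 + 80 + 80 + 85)/5 = 86.0 | 330/4 = 82.5 |

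On seven frequencies deletion moves the PTA by +4.3 and −3.6 dB. On the five common frequencies it moves it by +2.0 and −3.5 dB. Part of what is seen on seven frequencies comes from 250 and 8000 Hz, which have no aided counterpart.

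**The case against.** The strongest reply has four parts.

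**No bias is demonstrated.** A reader might infer that the rule biases the gain in every severe or SSD ear, or that it inflates the gain. The documents do not support either reading. The sign varies, and the shift is zero when all other frequencies are NR at the limit that would be substituted, as can happen in a profoundly deaf ear. This stands.

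**A VT level is not the truth.** It is a lower bound, and it need not be the audiometer's limit, which is how the SAP describes NR. Neither document says whether a level is recorded with VT, or that VT occurs only in the worst ears. This stands, so the PTA with VT substituted cannot be called the correct value. What remains is an inconsistency between two kinds of unheard result.

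**VT may not reach the primary gain.** The deletion rule covers AC, BC and aided tests, and VT entries on BC tests alone would not enter the gain. One also cannot assume that the aided PTA always keeps all five frequencies. This stands, and it is a reason to count VT results by test. It does not justify the rule for AC.

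**Substitution may be no better.** Against the five-frequency PTA with VT at its level (108.0 and 86.0 dB), seven-frequency deletion in the two invented ears is off by 2.0 and 1.0 dB, and seven-frequency substitution by 2.3 and 2.6 dB. Where measured thresholds are better than the limit, deletion also gives the smaller, more cautious gain. Both statements are correct. The first reflects the frequency mismatch and calls for a five-frequency analysis. The second fails where the other frequencies are NR at a higher limit, and the SAP does not offer it as a reason.

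**Conclusion.** The inconsistency is on the page: unaided NR is substituted, VT is dropped as if untested, and no planned analysis tests the VT rule. It can shift the unaided PTA and the primary gain in ears with AC VT results.

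- **Direction:** relative to the plan's own NR convention, gain falls when the other frequencies are better than the limit, is unchanged when they are all NR at that limit, and can rise when they are NR at a higher one.
- **Size:** several dB in an affected ear, such as 8.6 dB with two of seven frequencies VT, the rest at 70 dB and a 100 dB substitute. The cohort effect cannot be stated, because neither the VT count nor the VT level is given. The 0.9 to 2.6 dB range rests on an assumed 10% to 30% of ears.
- **Consequence:** with a 29 dB planning difference and 6 pairs needed, the overall significance test is unlikely to change. The effect is on the estimated gain, mainly in ears with severe loss and in the SSD subset. That VT results will concentrate there is audiological reasoning, not document text.

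This is worth correcting because it is cheap, not because it threatens the study's main conclusion.

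**What to change.** In SAP 7.6, handle an unaided VT result by the same rule as NR within each method:

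- **Method I:** use the recorded VT level, or the existing default (100 dB AC, 65 dB BC) if none was recorded.
- **Method II (SSD subset):** use the mean plus two standard deviations, as for NR.

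Keep only untested frequencies as missing, and say how a VT entry with a dB level fits the collected-value rule. The SAP has no NR substitution for aided tests to align with, so aided VT results stay outside this change.

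Report VT counts by test and frequency. As a sensitivity analysis, repeat the primary gain and the SSD subset with VT deleted. Run the comparison also on the five frequencies common to the unaided and aided tests (500 to 4000 Hz), so that the VT effect is not mixed with the seven-versus-five mismatch.

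The cost is a few sentences in the SAP, one count table and some extra runs on data already collected. The downside is that a few more PTA values will rest on a substituted lower bound; the analysis with VT deleted shows how much that matters.

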Safety Assessments	A review and assessment of all device-related Adverse Events (AE) collected retrospectively via chart review, and any prospective device-related AE that occur from the time of subject consent until the time of study exit.								
Statistics	
The primary effectiveness endpoints are the improvement in aided hearing from unaided hearing by the Sophono Alpha 2 MPO processor. This endpoint will be summarized by means of paired (samples) t-test or Wilcoxon signed rank sum test according to the normal or non-normal distribution as appropriate.
 
The primary safety endpoint is an assessment of all AEs (prospective or retrospective) that are directly attributable to the Sophono device (implant or processor). This endpoint will be the proportion of events reported with confidence interval (95%).
								

This document is electronically controlled. Printed copies are considered uncontrolled.

Confidential

5. Introduction

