6.2.1.2. Primary Efficacy Endpoint

The primary efficacy endpoint is the difference (gain) in the free-field pure tone audiometry assessed by pure tone average (PTA) unaided (AC) and aided (BC) by the Alpha 2 MPO processor.

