7.10.3 Secondary endpoint#1

The secondary objective#1 will be evaluated as the difference in the free-field pure tone audiometry assessed by PTA aided by Alpha 2 processor compared to the PTA aided by Alpha 2 MPO processor. The difference between Alpha 2 and Alpha 2 MPO measurements will be analyzed by means of paired (samples) t-test or Wilcoxon signed rank sum test according to the normal or non-normal distribution.

Table x - Difference in PTA by device (Audiogram Results Gain)

Figure x - PTA by device type

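### The SAP defines gain as an absolute difference with no order of subtraction, so, read literally, the reported gain, its mean and its interval could not show worsening

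*SAP*

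**What the plan says.** - **Derivation (SAP 7.6).** The whole rule for gain is "Absolute difference between PTA values". The row gives the unit (dB). It does not say which PTAs are subtracted, in what order, or which sign means benefit. The date-based rows of the same table each name two operands and an order.
- **Primary endpoint (SAP 7.10.1).** "The primary effectiveness endpoint is the absolute difference (gain) in the free-field pure tone audiometry assessed by PTA unaided (AC) and aided"; here the device is Alpha 2 MPO. The word therefore appears twice in the SAP and is not a single slip.
- **Primary endpoint (Protocol 6.2.1.2).** "The primary efficacy endpoint is the difference (gain) in the free-field pure tone audiometry", without *absolute*. The statistics entry of the protocol synopsis is directional: "improvement in aided hearing from unaided hearing by the Sophono Alpha 2 MPO processor".
- **Primary test (SAP 7.10.1).** "The difference between unaided and aided measurements will be analyzed by means of paired (samples) t-test or Wilcoxon signed rank sum test", chosen by normality.
- **Alpha 2 versus Alpha 2 MPO (SAP 7.10.3).** The text names the same two paired tests and does not use *absolute*. The title of its table reads, up to the closing bracket, "Difference in PTA by device (Audiogram Results Gain", so it carries the gain label.
- **Reporting (Protocol 13.4).** The mean change is to be shown with a 95% confidence interval.

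**The concern.** In a derivation table, the ordinary reading of an absolute difference is |a - b|. A programmer who codes that follows the specification, and the second-person checks in SAP Section 8 could confirm the code as correct. The result would be a gain variable that cannot be negative. A subject who hears worse with the processor would show the same gain as one who hears better by the same amount. The mean gain and its interval would be centred at or above zero whatever the truth.

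This conflicts with the directional endpoint in the protocol. It matters most for secondary objective 1, which asks which of two processors performs better. The documents give no expected size or sign for that difference, and individual differences could go either way.

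**Working it through.** **Step 1. The plan's own figure.** Protocol 13.1 gives 58.7 dB unaided and 29.7 dB aided, SD 8.2 dB in each condition, two-sided 5%, power 95%, and 6 pairs.
- The planning effect is 58.7 - 29.7 = 29.0 dB, already a signed difference, unaided minus aided.
- The SD of the paired difference is not given. It is 8.2 × √(2(1 - ρ)), with ρ, the unaided-aided correlation, assumed.
- Exact paired t-test (noncentral t): at ρ = 0 the SD is 11.6 dB, and 5 pairs give 98.2% power and 6 give 99.7%. At ρ = -0.5 the SD is 14.2 dB, and 6 pairs are needed (97.5%). At ρ = 0.25 or 0.5, 4 pairs suffice.
- So 6 pairs is reproduced at ρ = -0.5 and is enough at the higher correlations tried. A signed definition of gain does not change it.

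**Step 2. The literal rule on one subject.** Unaided 50 dB, aided 60 dB: |50 - 60| = 10. Unaided 60 dB, aided 50 dB: |60 - 50| = 10. The rule scores a 10 dB worsening and a 10 dB improvement alike.

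**Step 3. Effect on the primary mean.** If the signed difference d is normal with mean μ and SD σ, then

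E|d| = σ√(2/π) · exp(-μ²/2σ²) + μ(1 - 2Φ(-μ/σ)).

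With μ = 29 and three assumed SDs:
- σ = 11.6: 9.26 × exp(-3.125) + 29 × (1 - 2 × 0.0062) = 0.41 + 28.64 = 29.05 dB. The shift is about 0.05 dB, and 0.6% of true gains fall below zero.
- σ = 8.2: 29.0 dB, with 0.02% below zero.
- σ = 15: 29.3 dB, with 2.7% below zero.

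**Step 4. Effect where the difference is small.** This applies to Alpha 2 versus Alpha 2 MPO only if that table uses the derived variable. The SDs are assumptions. The value 5 dB has no source in the documents. The value 8.2 dB is the SD within one condition and equals the SD of differences only at ρ = 0.5.
- True difference 0: E|d| = σ√(2/π), which is 5 × 0.798 = 4.0 dB or 8.2 × 0.798 = 6.5 dB.
- True difference +3 or -3 dB, SD 5: 3.99 × exp(-0.18) + 3 × (1 - 2 × 0.274) = 3.33 + 1.35, about 4.7 dB in both cases.
- True difference -5 dB: 5.8 dB at SD 5 and 7.7 dB at SD 8.2, both reported as positive.

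**Step 5. The tests.** A paired t-test on two PTAs uses the mean of the signed differences, and the signed-rank test uses the sign of each difference. Run on the two measurements, as SAP 7.10.1 and 7.10.3 describe, neither is altered by the gain definition. The SAP does not say that the tests and the derived gain are the same quantity.

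**The case against.** The strongest reply is that *absolute* was meant in its other common sense: a difference in dB rather than a percentage. That contrast is live, because Protocol 13.1 summarises the literature as an average improvement of 50%, and SAP 7.6 labels the variable in dB. The reading is plausible, but the SAP does not state it. It makes this an ambiguity to resolve, not proof of wrong programming.

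A reader might infer that the analysis would almost always declare benefit. A one-sample t-test on unsigned differences would do so: in simulation with no true difference it rejected in essentially all trials at 72 pairs, against about 5% for signed values. The documents do not specify that test. They specify paired tests on the two measurements. A signed-rank test on unsigned values would be meaningless, since all ranks would share one sign. The high rejection rate is therefore not a property of this plan.

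A reader might also infer that the Alpha 2 versus MPO table certainly uses the unsigned variable. That rests only on the table's title, since the text of SAP 7.10.3 says difference without *absolute*.

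Other outputs limit the harm. SAP 7.10.3 plans a figure of PTA by device, SAP 7.7 tabulates the prospective audiograms, and the separate table specification cited in SAP 10.1, not available here, may fix a sign. These reduce the risk but do not repair the definition.

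**Conclusion.** The point holds as a defect in a derivation rule. The SAP's gain has no direction, the protocol's endpoint does, and a literal reading makes every gain non-negative. What is at risk is the reported gain values, their mean and their interval, not the p-values of the tests as specified.

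For the primary endpoint the practical effect is negligible: about 0.05 dB on 29.0 dB at an assumed SD of differences of 11.6, and about 0.3 dB at an SD of 15. The inference that the primary effectiveness result is compromised is not supported. Where differences are near zero, the distortion could be as large as the effect of interest: 4.0 to 6.5 dB of apparent gain with no true difference, and no way to tell which processor is better from that number. This second result depends on the assumed SDs of 5 and 8.2 dB, on normal differences, and on the Alpha 2 versus MPO table using the derived variable.

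**What to change.** In SAP 7.6 and 7.10.1:
- Define gain for the primary endpoint as unaided PTA minus PTA aided by Alpha 2 MPO, with positive values meaning improvement.
- For secondary endpoint 1, define the difference as Alpha 2 PTA minus Alpha 2 MPO PTA, with positive values favouring MPO, and repeat this in SAP 7.10.3.
- Delete *absolute*, or keep it with a statement that it means dB rather than percent.
- State that the test, the mean and the 95% confidence interval all use this signed variable.
- Check that the separate table specification follows the same convention.

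The cost is SAP wording and, if the unsigned form has already been coded, a small change to the program. Sample size, data collection and choice of tests are unchanged.

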10.4. Subject Consent

Prior to study enrollment and before any study visits are initiated, all subjects must document their consent by signing an IC and Research Authorization Form. The Study Investigator or his/her authorized designee will conduct the informed consent process during which the subject will have the opportunity to ask questions and receive answers about the study. Subjects will be made aware that the study includes a medical chart review, as well as an in-office follow-up visit, and they should be willing to comply with the study requirements to be available for study visits. If they decide not to come in for the in-office follow-up visit the data from the medical chart review will still be used in data analysis.

A copy of the signed IC and Research Authorization will be provided to the subject, and the original signed version will be retained in the site's study files. The site will record the date of consent in the CRFs.

Obtaining data from a subject's medical chart or a follow-up visit without obtaining informed consent is a protocol violation and is to be recorded in the Protocol Deviation CRF and reported to the Sponsor, as well as the respective IRB/IEC as soon as possible, **but no later than five (5) working days after the event occurred, or sooner if required by the IRB/IEC.**

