13.3. Safety endpoint

Event rates, weighted for center, will be displayed together with their 95% confidence interval (95%CI); for each possible sub-group, analyses will be compared by means of a mixed Poisson model, with center included as random effect. In the presence of over dispersion, negative binomial regression will be used. Over dispersion will be assessed both with a goodness-of-fit test and a likelihood ratio test for $\alpha=0$. The incidence rate ratio (IRR) and 95%CI will be reported [IRR=rate group1 / rate group2]. The exposure time (days/months) will be computed from implantation to the date of the follow-up visit for each patient [(data end – data in)/30.4].

Specific events will be analyzed using survival analysis. The analysis will be supported by a Kaplan Meier curve indicating the number of patients at risk and comparison of curves will be done using the generalized Log-Rank Test where appropriate. The exposure time (months) will be computed from the date of the implantation to the date of the last available follow-up or date of event: [(data end – data in)/30.4].

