5.3 Overall study design and plan-description

After informed consent is collected, the study will consist of a retrospective medical chart review to collect data on AEs for all subjects. A prospective clinic visit for subjects still implanted with the Sophono implant will be conducted to evaluate the subject's implant site and conduct hearing tests, along with a QOL and satisfaction self-assessment.

All subjects will be screened for study eligibility. A qualified member of the investigational site's research team will review the inclusion and exclusion criteria to screen each subject. Subjects will be considered enrolled into the study when they have both:

[figure not shown]
- Been informed of the study design, objectives, risks and benefits
- Confirmed interest in participation by signing an IC and Research Authorization Forms

Any subject who currently has or who has had the Sophono implant (including those who have been explanted) may be enrolled.

A Screening and Enrollment Log will be maintained for all subjects. For screen-fail subjects, a reason for failure will be noted.

Clinical data will be collected during:

- a retrospective review of the subject's medical chart will be performed to gather and report data on subject surgical history, reportable AEs from the time of implantation to time of chart review, previous QOL scores, and previous audiometric testing results for the Sophono processors.
- an in-office ENT exam will be conducted to gather and report data on the ear and implant site for skin complications, potential AEs and Sophono system satisfaction and QOL questions. During the in-office visit Audiology testing will be performed to collect data on: Basic Sound Field Audiology thresholds at octave intervals, Speech Reception Threshold, Word Recognition Thresholds and Hearing in Noise.

Figure x – Flow Chart

Data collection requirements are summarized in the following table:

Table x – Data Collection Requirements

Data	Baseline	Retrospective	Prospective	Study Exit
Informed Consent	X			
Inclusion/Exclusion Criteria Evaluation	X			
Demographic	X			
Medical History (including Procedure)	X	X		
Audiogram		X	X	
Speech Recognition Threshold		X	X	
Word Recognition Threshold		X	X	
Quality of Life Scores (including Additional Items)		X	X	
Product Satisfaction			X	
ENT Exam			X	
Adverse Events		X	X	X
Protocol Deviations	X		X	X

6 Determination of Sample Size

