7.10 Evaluation of Objectives

In this section, detailed information about each objective is included together with calculations and derivations of outcome parameters (see table in section 7.6), analysis methods, datasets analyzed (FAS or PPS) and additional analyses where applicable.

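### SAP 7.6 computes time to first AE backwards (evaluation date minus AE date), so the planned Kaplan-Meier outputs would be wrong if programmed as written

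*SAP*

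**What the plan says.** SAP 7.10.1 states, under the primary safety endpoint, "A time to first Adverse Event will be performed using survival analysis". It lists a Kaplan-Meier figure and a Kaplan-Meier table for the first implant-related AE, with log-rank comparison of groups where appropriate. It gives no time origin and no censoring rule of its own.

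The opening paragraph of SAP 7.10 says that the section covers "calculations and derivations of outcome parameters (see table in section 7.6"), so the derivation is the one in SAP 7.6. There, Time to first AE (days) is "Study Evaluation- First AE occurrence date". The footnote to that row adds only "if more than one procedure or event, consider the date of the first one". It selects the event and sets neither an origin nor a censoring date.

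Protocol 13.3, in its paragraph on survival analysis, computes the time "from the date of the implantation to the date of the last available follow-up or date of event" and divides days by 30.4 to get months.

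In the same SAP table, Device Exposure is the study evaluation or explant date minus the procedure date, and Time to explant is the explant date minus the procedure date. Both start at the procedure.

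**The concern.** Subtracting the AE date from the evaluation date gives how long ago the event happened when the subject was evaluated. It does not give how long after implantation the event came. The recorded time therefore depends on when the subject was evaluated. In an ambispective study, where implant duration only has to reach three months, that date can differ widely between subjects.

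The row also has a coverage gap. A subject without an AE has no AE date, so the row yields nothing to censor on. SAP 7.6 does not say which date Study Evaluation is. If it is the clinic visit, explanted subjects have none, since "A prospective clinic visit for subjects still implanted with the Sophono implant will be conducted". Nor do subjects who decline the visit, although for them "the data from the medical chart review will still be used in data analysis". The Device Exposure row has the explant date to fall back on; this row has no fallback.

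At stake are one Kaplan-Meier figure, one Kaplan-Meier table and any log-rank test. The primary AE proportion or rate and its 95% confidence interval do not use the variable.

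The same table contains a lesser slip. Time Diagnosis-Implant, labelled in months, is "Diagnosis date-Date of Implant)/365.25". This is negative whenever diagnosis precedes implantation, and the divisor gives years. The variable is descriptive only.

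**Working it through.** The documents give no event count, power or expected curve for this analysis, so there is no figure of the plan's own to reproduce. The check compares the two definitions.

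**1. Algebra.** Let T be the time from implantation to first AE (Protocol 13.3), and F the time from implantation to evaluation. The SAP 7.6 row records T* = F − T. The two agree only when T = F/2, that is, when the AE falls exactly midway between implantation and evaluation.

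**2. Single subjects** (dates are examples).

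| AE day (T) | Evaluation day (F) | Protocol 13.3 | SAP 7.6 (F − T) |
|---|---|---|---|
| 20 | 365 | 20 | 345 |
| 20 | 1095 | 20 | 1075 |
| 365 (found at visit) | 365 | 365 | 0 |
| 30 | 730 | 30 | 700 |
| 700 | 730 | 700 | 30 |
| 740 (before study exit) | 730 | 740 | −10 |

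The last row is possible because the Protocol synopsis collects device-related AEs from consent to study exit, which can be later than the visit.

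**3. Cohort illustration.** The only input from the documents is the 14% AE incidence in Protocol 13.1. That figure is for any AE, whereas the Kaplan-Meier outputs are for implant-related AEs. Everything else is assumed:
- 400,000 simulated subjects per scenario, with follow-up uniform on 91 to 1825 days.
- 0, 25 or 50% of AEs dated at the visit.
- 70% or 40% of the remaining AEs in the first 90 days, the rest uniform to the end of follow-up.
- AE-free subjects censored at full follow-up under both definitions. The SAP row does not supply this, so the as-written curves borrow the Protocol's censoring rule.

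| Early share | Visit-dated share | 90-day correct | 90-day as written | 365-day correct | 365-day as written |
|---|---|---|---|---|---|
| 70% | 0% | 9.9% | 1.1% | 11.8% | 4.3% |
| 70% | 25% | 7.4% | 4.4% | 9.5% | 6.7% |
| 70% | 50% | 4.9% | 7.6% | 7.1% | 9.1% |
| 40% | 0% | 5.7% | 1.8% | 9.7% | 5.8% |
| 40% | 25% | 4.3% | 4.9% | 7.9% | 7.9% |
| 40% | 50% | 2.8% | 8.0% | 6.1% | 10.0% |

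With 70% early and no visit-dated AEs, the rank correlation between true and recorded event times is −0.37. Because F varies, the order is scrambled rather than strictly reversed.

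A second simulation used 20,000 subjects, follow-up uniform on 91 to 1460 days, exponential onset and no visit-dated AEs. At 90 / 365 / 730 days it gave:
- mean onset 60 days: 10.5 / 13.7 / 13.7% correct against 0.4 / 3.4 / 8.8% as written;
- mean onset 180 days: 5.4 / 12.1 / 13.7% correct against 0.7 / 3.8 / 9.2% as written.

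**4. Diagnosis-to-implant row.** Take a diagnosis 730.5 days before implantation. As written: −730.5/365.25 = −2.0, under a heading in months. Corrected: 730.5/30.4 = 24.0 months.

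**The case against.** The strongest reply is that this is a visible drafting slip that would not survive programming. The variable's name says what is meant. The footnote mentions a procedure although the formula contains no procedure date, which suggests a dropped term. A literal program would leave every AE-free subject without a time. SAP section 8 requires a second programmer or statistician to validate the derived datasets and tables, and a second statistician to review the results. SAP 10.1 points to a separate output specification that may set the variable correctly. This makes a wrong published curve less likely, but it does not repair the SAP. Validation checks code against the specification, and here the specification is what is wrong.

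A second reply is that a censoring rule can be assembled. SAP 7.8 runs device exposure to the last evaluation, or explant, for the full analysis set. SAP 7.1.3 keeps dropouts' data up to their last collection. Protocol 13.3 names last available follow-up. This stands in part: the material exists, and the gap for subjects without a visit depends on how Study Evaluation is read. None of it corrects the formula, and the row does not refer to it.

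Third, the cohort figures rest on assumed timing, and one of the six scenarios shows no difference at 365 days (7.9% against 7.9%). That is fair. They show that the error can be large in either direction; they do not predict its size here.

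Two smaller points do not change the conclusion. Protocol 13.3 words its rule for specific events, but it is the Protocol's only survival-time definition. SAP 7.13 allows departures because of data availability, but procedure and AE dates are both already inputs to the 7.6 table.

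**Conclusion.** The concern holds. The SAP 7.6 formula for time to first AE measures the wrong interval and conflicts with Protocol 13.3 and with the neighbouring SAP rows. This is an error as written, not a missing detail. The reversal follows from the definitions and needs no assumption. Its effect on the cohort curve cannot be sized from the documents: under the assumptions above, early incidence could be badly understated, overstated or, by coincidence, about right.

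The consequence is limited to the time-to-first-AE figure, table and any log-rank test, and only if the row is programmed literally. The primary safety proportion or rate, its confidence interval and the sample size are untouched. The row should be corrected before the analysis datasets are built.

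**What to change.** In SAP 7.6:
- Set Time to first AE (days) to first AE date minus procedure date.
- Censor AE-free subjects at last available follow-up date minus procedure date, as in Protocol 13.3. Add one sentence naming that date for subjects with no prospective visit, both those explanted and those who did not attend.
- State one time unit, since the SAP row uses days and Protocol 13.3 uses months.
- Set Time Diagnosis-Implant (months) to (implant date minus diagnosis date)/30.4.

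If the sponsor prefers to censor at explant, the SAP should state it as a deliberate choice, because Protocol 13.3 does not include it. That is a separate analytic decision and not part of this correction.

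The cost is two lines of SAP text with the matching derivation code, plus the sentence on the follow-up date and a stated unit. No endpoint, data collection or sample size changes.
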